### 7.7 Secondary analyses

#### 7.7.1 Efficacy

To evaluate how estimated PV (ePV) and estimated total blood volume (eTBV) assessments on days 1 and 3 (by Nadler's formula, Kaplan-Hakim formula) predict measured PV (mPV; as assessed by FAST methodology) and measured TBV (mTBV; calculated from mPV and measured hematocrit) at these time points, linear regression models with the measured values at a given day as dependent variable and the estimated version as independent variable will be generated. The models will be adjusted for BMI, weight, and height separately.

Further, Bland-Altman plots will be generated comparing the estimated and measured parameters separately for day 1 and day 3. The defined limits of agreement are  $\pm 500\text{ml}$  for TBV and  $\pm 300\text{ml}$  and for PV. The amount of values within 15% and within 30% of the measured values will also be determined. In addition, the diagnostic test accuracy including 95% confidence interval as proposed by Obuchowski (Obuchowski, 2005) will be calculated. The interpretation for a continuous reference standard is as follows: Of two randomly chosen patients, the diagnostic accuracy is the probability that the patient with the higher reference standard result has a higher diagnostic test result than the patient with the lower reference standard test result. In the case of the study, the measured PV and TBV will act as reference standard while the estimated versions serve the diagnostic test.

To evaluate how a clinical evaluation on days 1 and 3 predicts mPV and mTBV at these time points, linear regression models will be used.

Depending on the amount of available information and distribution, the following parameters will be considered for the analysis in the order of appearance: hematocrit (only PV), mean arterial blood pressure, BMI (only PV), weight, height (BMI, weight, height will be entered in 3 separate models), age, gender, NYHA stage, respiratory rate, edema grade, presence of pulmonary rales, jugular venous congestion. At least 10 observations will be needed per parameter that need to be estimated. Bland-Altman plots, frequencies within 15% and 30%, and diagnostic accuracy will be evaluated as stated before.

To evaluate whether eGFR calculation by the CKD-EPI formula and sMDRD formula on days 1 and 3 provides an accurate estimate of measured GFR (mGFR; assessed by FAST methodology) in heart failure patients undergoing active fluid management, linear regression models with the measured value at a given day as dependent variable and the estimated version as independent variable will be generated. The models will be adjusted for mPV and mPVS. Further, Bland-Altman plots will be generated comparing the estimated and measured parameters separately for day 1 and day 3. The defined limits of agreements are  $\pm 6\text{ml/min}$ . Diagnostic accuracy including frequencies of values between 15% and 30% of the measured value will be determined as mentioned before.

To evaluate whether patients with a low mGFR/eGFR ratio on days 1 and 3 are at higher risk of developing AKI within the following 72 (day 1) and 48 (day 3) hours, logistic regression models with the AKI status as dependent variable and mGFR/eGFR ratio as independent variables will be generated. The models will be adjusted for mPVS, mTBVS. Three different versions of the mGFR/eGRF ratio will be evaluated: ratio  $< 1$ ; ratio  $<$  first quartile; ratio as continuous parameter.

To evaluate whether ranges of mPVS (low mPVS ( $< -10\%$ ), normal mPVS ( $-10$  to  $+10\%$ ), high mPVS ( $> +10\%$ )) and/or mTBVS (low mTBVS ( $< -10\%$ ), normal mTBVS ( $-10$  to  $+10\%$ ), high mTBVS ( $> +10\%$ )) on days 1 and 3 are associated with subjectively reported symptoms (current PGA  $> 15$ , current dyspnea  $> 15$ , current dizziness  $> 15$ , current nausea  $> 15$ ) determined using patient symptom assessment sheets within the following 24-48 hours, a logistic regression

---

model with occurrence of symptoms (PGA, dyspnea, dizziness, nausea) as dependent variable and the categorized measured value (mPVS, mTBVS) as independent variables will be generated. The models will be adjusted for mean arterial pressure.

To evaluate whether patients with low mPVS ( $< -10\%$ ) or low mTBVS ( $< -10\%$ ) on day 1 or on day 3 are at risk of developing low-output complications within the next 24-48 hours (subjectively reported dizziness  $> 15$ , nausea  $> 15$ , PGA  $< 25$ , hypotension (Systolic  $< 100$ , diastolic  $< 60$  mmHg), need for iv-fluid therapy), logistic regression models using mPVS and mTBVS as independent variables will be used.

To evaluate whether patients with a high mPVS ( $> +10\%$ ) or a high mTBVS ( $> +10\%$ ) on day 1 and/or day 3 are at risk of being refractory to diuretic therapy (defined as any dosage increases of furosemide i.v. dose equivalent, adding thiazide after day 1, require ultrafiltration/RRT within the next 24-48 hours, fail to improve subjectively in PGA and dyspnea scales, fail of mean weight loss during the study period Day 1-Day 5 of at least 0,5 kg/d) logistic regression models using mPV and mTBV as independent variables will be used.

To evaluate whether the changes of ePV (using relative and absolute change as well as the Strauss' formula) and eTBV (using relative and absolute change) from day 1 to day 3 adequately reflects the changes of mPV and mTBV Bland-Altman plots will be generated. These plots will be analysed exploratory, since no appropriate values for limits of agreements are available. The amount of values within 10% and within 30% of the measured values will also be determined. In addition, the diagnostic test accuracy including 95% confidence interval as proposed by Obuchowski will be calculated.

To evaluate whether the change of mPV and mTBV and changes of mPVS and mTBVS from day 1 to day 3 as well as the mPVS and mTBVS on Day 1 and Day 3 is predictive of the remaining length of stay at the given day (i.e. remaining length of stay starting with day 1 or with day 3), dialysis/ultrafiltration requirement, or rehospitalization within 30 days, or mortality, linear (remaining length of stay), logistic (dialysis/ultrafiltration, rehospitalization within 30 days) or Cox-regression models (mortality) will be utilized using changes of mPV and mTBV from day 1 to day 3 (first model), changes of mPVS and mTBVS from day 1 to day 3 (second model), and mPVS and mTBVS at day 1 (third model) and day 3 (fourth model) as independent variables.

To evaluate whether the percentage changes of mGFR from day 1 to day 3 ( $< 0$  vs.  $\geq 0$ ; continuous) predicts the percentage changes of eGFR from day 2 to day 4 (CKD-EPI formula only;  $< 0$  vs.  $\geq 0$ ; continuous), a logistic as well as a linear regression model will be used.

The same will be done to investigate the changes in eGFR from day 1 to day 3 (all formulas) as the dependent variable. Further, exploratory Bland-Altman plots without predefined limits of agreement will be created.

To evaluate whether patients with a high PVS or TBVS on Day 1 ( $> +10\%$ ) and a decreasing PVS

or TBVS between Day 1 and 3 had significantly different percentage change of mGFR between Day 1 and Day 3 compared to patients with a high PVS or TBVS and an increasing PVS between Day 1 and 3, t-Tests or Mann-Whitney-U-tests will be used depending on the distribution of the values.

To evaluate whether Patients with a low PVS or TBVS on Day 1 (<-10%) and an increasing PVS or TBVS between Day 1 and 3 had significantly different percentage change of mGFR between Day 1 and Day 3 compared to patients with a low PVS or BCS and a decreasing PVS between Day 1 and 3, t-Tests or Mann-Whitney-U-tests will be used depending on the distribution of the values.

To evaluate whether patients with an improving (i.e. increasing) mGFR from day 1 to day 3 differ significantly from patients with a worsening (i.e. decreasing) mGFR regarding baseline characteristics (see chapter 4.1), mPVS, mTBVS, ePVS, eTBVS, and remaining length of stay appropriate tests depending on the distribution will be used (t-Test or Mann-Whitney-U-test for continuous variables and chi-square tests or Fisher-Boschloo-tests for categorical variables).

To evaluate whether disagreement between the physicians response to the question what they thought the intravascular volume of the patient was doing (increasing, decreasing, no change, treating physicians assessment Day 3) and the direction of measured change in TBVS is associated with a longer remaining length of stay, a t-test or Mann-Whitney-U-test depending on the distribution will be used. A measured change in TBVS of more than 5% between Day 1 and 3 was determined as a significant change.

To evaluate (by an adjudication committee) whether clinical decision making would have been affected by adding FAST GFR and PV measurements to clinical routine, the following questions were to be answered:

- How would you alter the intensity of Diuretic Therapy given on Day 1 and Day 3?
- How would you alter the intensity of RAASI Therapy given Day 1 and Day 3?  
How would you alter the intensity of Beta Blocker Therapy given Day 1 and Day 3?
- How would you alter the intensity of other GDMT given Day 1 and Day 3?

To evaluate this endpoint an adjudication committee will be convened to analyse the outputs of the study after its completion. The goal of the adjudication committee is to the best of their ability describe any changes in treatment they would have made to each patient had the mPV and mGFR metrics been available during the episode of care. No clinical decisions will be made based on the results generated by the FAST PV and mGFR Technology as results will not be made available to the treating physicians and will only be released to the adjudication committee after the last patient has been discharged.

The scale to define the intensity of changes reaches from 1 to 5 meaning from much less intense to much more intense (3 is no change).

Absolute and relative frequencies of the changes to the questions specified above will be calculated for the whole assessment and separately for Day 1 and Day 3.

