### **Secondary objectives:**

- To evaluate how estimated PV (ePV) and estimated total blood volume (TBV) assessments on days 1 and 3 (by established measures such as Nadler's formula or Metropolitan Life Tables) predict measured PV (mPV; as assessed by FAST methodology) and measured TBV (mTBV; calculated from mPV and measured hematocrit) at these time points. Simple linear regression models will be generated and potentially adjusted for relevant confounders.
- To evaluate how a clinical evaluation (including a reasonable subset of the variables age, gender, BMI, hematocrit, edema grade, presence of pulmonary rales, presence of jugular venous congestion, arterial blood pressure, NYHA stage, respiratory rate) on days 1 and 3 predicts mPV and mTBV at these time points. Optimal linear models will be chosen by comparing the results of different variable selection models for the corresponding linear model (backward selection based on p-Values and Akaike Information Criterion, best subset selection etc.).
- To evaluate whether eGFR calculation by the CKD-EPI formula on days 1 and 3 provides an accurate estimate of measured GFR (mGFR; by assessed by FAST

methodology) in heart failure patients undergoing active fluid management. Simple linear regression models will be generated and potentially adjusted for relevant confounders.

- To evaluate whether patients with a low mGFR/eGFR ratio on days 1 and 3 are at higher risk of developing AKI within the following 48-72 hours. Logistic regression models will be generated and potentially adjusted for other relevant confounders.
- To evaluate whether ranges of mPV (low mPV, normal mPV, high mPV) and/or mTBV (low mTBV, normal mTBV, high mTBV) on days 1 and 3 are associated with subjectively reported symptoms (PGA, dyspnea, dizziness, nausea) determined using patient symptom assessment sheets within the following 24-48 hours. Logistic regression models will be generated and potentially adjusted for other relevant confounders. Associations will be assessed by chi-square interaction tests and by Spearman's correlation coefficient.

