## 7.2 Derived Parameters

The following formulas will be used for determination of estimated and measured TBV, ideal TBV, estimated and measured total blood volume status (eTBVS and mTBVS), ePV, estimated PV change, ideal PV, estimated and measured plasma volume status (ePVS and mPVS), and eGFR on day 1 and day 3:

Nadler formula for eTBV (Sharma & Sharma, 2020):

- Men:  $eTBV [L] = (0.3669 \times \text{Height [m]}^3) + (0.03219 \times \text{Weight [kg]}) + 0.6041$
- Women:  $eTBV [L] = (0.3561 \times \text{Height [m]}^3) + (0.03308 \times \text{Weight [kg]}) + 0.1833$

mTBV will be calculated as follows:

- $mTBV [mL] = mPV [mL] / (1 - \text{hematocrit [\%]} / 100)$

Lemmens-Bernstein-Brodsky formula for ideal TBV (iTBV) (Lemmens, Bernstein, & Brodsky, 2006):

- $iTBV [mL/kg] = 70 / [\text{sqrt}(\text{body mass index}/22)]$  – the lowest body weight during the days 1 to 5 will be used for calculation of BMI
- $iTBV [mL] = iTBV [ml/kg] \times \text{weight [kg]}$  – the lowest body weight during the days 1 to 5 will be used for calculation

Estimated and measured total blood volume status:

- $eTBVS [\%] = \text{Percentage change from iTBV: } (eTBV - iTBV) / iTBV$
- $mTBVS [\%] = \text{Percentage change from iTBV: } (mTBV - iTBV) / iTBV$

Kaplan-Hakim Formula for ePV (Ling et al., 2015):

- Men:  $ePV [mL] = (1 - \text{hematocrit [\%]}) \times [1530 + (41 \times \text{weight [kg]})]$
- Women:  $ePV [mL] = (1 - \text{hematocrit [\%]}) \times [864 + (47.9 \times \text{weight [kg]})]$

Strauss formula for plasma volume change (Strauss, Davis, Rosenbaum, & Rossmeis, 1951):

- $PV\_2/PV\_1 \times 100 [\%] = \text{hemoglobin\_1 [g/dL]} / \text{hemoglobin\_2 [g/dL]} \times (1 - \text{hematocrit\_2 [\%]}) / (1 - \text{hematocrit\_1 [\%]}) \times 100$

Plasma volume change will also be calculated via the ratios of ePV by the Kaplan-Hakim-Formula

Harrison formula for ideal PV (iPV) (from Ling 2015):

- Men: iPV [mL] = 39 [mL/kg] × weight [kg] – the lowest body weight during the days 1 to 5 will be used for calculation
- Women: iPV [mL] = 40 [mL/kg] × weight [kg] – the lowest body weight during the days 1 to 5 will be used for calculation

Estimated and measured plasma volume status (ePVS and mPVS):

- ePVS [%] = Percentage change from iPV: (ePV - iPV)/iPV
- mPVS [%] = Percentage change from iPV: (mPV - iPV)/iPV

The eGFR will be calculated using CKD-EPI formula (Levey et al., 2009):

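### SAP 7.7.1: adjusting the measured-on-estimated volume regressions for weight (both formulas) or height (Nadler) shows what a formula adds beyond its own input, not how well it predicts

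*SAP*

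**What the plan says.** The aim in SAP 7.7.1 reads: "To evaluate how estimated PV (ePV) and estimated total blood volume (eTBV) assessments on days 1 and 3 (by Nadler's formula, Kaplan-Hakim formula) predict measured" values, that is, mPV and mTBV. The method is "linear regression models with the measured values at a given day as dependent variable and the estimated version as independent variable will be generated". The next sentence is "The models will be adjusted for BMI, weight, and height separately". With two estimates, three covariates and two days, that makes 2 × 3 × 2 = 12 adjusted models.

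SAP 7.2 defines the estimates. Nadler eTBV is computed from height cubed and weight, with sex-specific coefficients. Kaplan-Hakim ePV is (1 − hematocrit) times a linear function of weight, again with sex-specific coefficients. Height does not enter Kaplan-Hakim, and BMI enters neither formula directly.

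For the same objective, protocol section 14 (secondary objectives) has: "Simple linear regression models will be generated and potentially adjusted for relevant confounders". SAP section 8 lists the changes from the protocol. It says covariates will be a fixed set chosen on clinical expertise, but does not explain why body-size inputs are adjusted for here. The SAP does not say which slope, adjusted or unadjusted, answers the objective.

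**The concern.** The question is one of prediction: if a clinician computes eTBV or ePV, how close is it to the measured value? A formula's inputs are not confounders of that question, because they are what the formula consists of. Once weight is held fixed, eTBV can vary only through height and sex, and ePV varies mainly through hematocrit and sex. The coefficient then answers a different question, namely what the formula contributes beyond weight, and answers it less precisely.

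At stake is how the regression results are read. The same formula could show slopes that differ widely between the three adjusted models, and the plan gives no rule for which of them speaks to the objective.

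**Working it through.** The documents give no figure for this analysis, so there is nothing to reproduce. The check takes the formulas from SAP 7.2 and N = 50 from the SAP sample size section.

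**Assumptions not in the documents.** 65% men; mean height 1.76 m (men) and 1.63 m (women), SD 0.07; mean weight 90 kg and 76 kg, rising 0.6 kg per cm of height above the sex mean, with a further SD of 12, 18 or 24 kg; hematocrit 0.38, SD 0.055, used as a fraction; residual SD of measured volume 800 mL (TBV) and 500 mL (PV).

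**Step 1: overlap of each estimate with each covariate.** VIF = 1/(1 − R²), where R² is the share of the estimate's variance explained by the covariate. Ranges are over the three weight SDs (200,000 simulated patients each).

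| Estimate | Covariate | R² | VIF |
|---|---|---|---|
| Nadler eTBV | weight | 0.78–0.82 | 4.6–5.6 |
| Nadler eTBV | height | 0.42–0.70 | 1.7–3.3 |
| Nadler eTBV | BMI | 0.17–0.46 | 1.2–1.9 |
| Kaplan-Hakim ePV | weight | 0.68–0.84 | 3.1–6.2 |
| Kaplan-Hakim ePV | BMI | 0.38–0.70 | 1.6–3.3 |
| Kaplan-Hakim ePV | height | 0.09–0.21 | 1.1–1.3 |

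A separate simulation gave weight VIFs of about 5–6.6 for eTBV and 2.9–6.1 for ePV. The combined ranges are 4.6–6.6 and 2.9–6.2.

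**Step 2: precision at N = 50, weight SD 18 kg, formula right apart from noise.** The sampling SD of the unadjusted slope is approximately residual SD / (√N × SD of the estimate). The SD of the estimate is 904 mL for eTBV and 598 mL for ePV.

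- eTBV: 800 / (7.07 × 904) = 0.125. Adjusting for weight (VIF 4.9) multiplies it by √4.9 = 2.2, giving 0.28.
- ePV: 500 / (7.07 × 598) = 0.118. Adjusting for weight (VIF 4.6) multiplies it by √4.6 = 2.1, giving 0.25.

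Simulation with 3,000 trials agrees: 0.13 rises to 0.29 for eTBV and 0.12 to 0.26 for ePV. The mean slope stays at 1.01 and 1.00.

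**Step 3: interpretation when measured volume tracks weight only.** Let measured volume = k × weight + noise, with k = 60 mL/kg for TBV and 36 mL/kg for PV. Given weight, the estimate then carries no further information, so its adjusted slope is zero by construction. Mean slopes from the simulation:

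| Estimate | Unadjusted | + weight | + height | + BMI |
|---|---|---|---|---|
| Nadler eTBV | 1.13 | 0.00 | 1.69 | 0.73 |
| Kaplan-Hakim ePV | 1.03 | −0.01 | 0.99 | 0.60 |

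In this scenario the formula still predicts. It shares 79% (eTBV) and 78% (ePV) of its variance with weight, which is the whole systematic part of the measured volume. The weight-adjusted slope is nevertheless nominally significant in only 4–5% of trials.

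**The case against.** Much of the other side stands.

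- The same section plans Bland-Altman plots by day, the share of values within 15% and 30%, and the Obuchowski accuracy with its confidence interval. No covariate adjustment is stated for any of them, and they address prediction directly. SAP 7.1 also makes all analyses descriptive. A reader might infer that the whole objective is compromised; it is not.
- An unadjusted model may already be intended. The SAP first describes the model with the estimate alone and adds adjustment in a second sentence. The protocol starts from simple regression, and SAP section 8 does not list dropping it. The text still does not say that the unadjusted result will be reported or will lead.
- A reader might infer that all the adjusted models are spoiled. Height is not a Kaplan-Hakim input, so that model is nearly unaffected, and BMI has a mild effect on eTBV. The covariates enter one at a time, so every model can be fitted.
- A reader might infer that a well-calibrated formula would look non-predictive. Under the residual SDs assumed above, the weight-adjusted slope of a correct formula still excluded 0 in 93% (eTBV) and 95% (ePV) of trials, and in about 89–96% when the simulation was repeated separately.
- The inflation can be put as 50 patients being worth about 50/4.9 ≈ 10. That describes one coefficient in the weight-adjusted models, not the objective.

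It can also be argued that a slope falling to zero is informative, because it shows that the formula's other terms add nothing in these patients. That is true, but it is a different question from the stated one, and the SAP does not give it as the purpose.

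**Conclusion.** The concern holds in a limited form. The weight-adjusted slopes for both estimates, and the height-adjusted slope for eTBV, do not measure how well the formulas predict. This follows from the definitions in SAP 7.2 and needs no assumption.

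The size does rest on assumed body-size distributions and residual SDs: a weight VIF of about 4.6–6.6 for eTBV and 2.9–6.2 for ePV, hence roughly a doubling of the slope's sampling SD at N = 50. A correct formula loses precision but not its expected slope of 1. The slope misleads when the formula's terms are wrongly weighted for these patients, and whether they are is what the objective is meant to find out. The damage is confined to the regression part of one descriptive secondary objective. The change is worth making because it costs almost nothing.

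**What to change.** In SAP 7.7.1, state that the unadjusted regression of measured on estimated volume is the regression result for this objective. Report, for each estimate and day, the intercept and slope with 95% confidence intervals read against 0 and 1, the R² and the residual SD.

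Label the weight-, height- and BMI-adjusted models as exploratory analyses of where the formula errs. A more direct version of the same idea is to regress measured minus estimated volume on weight, height or BMI, so that each coefficient shows how the error changes with body size.

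The cost is a few sentences of SAP wording before the analysis starts. No new data are needed, the unadjusted model adds four simple fits (two estimates × two days), and the agreement measures stay as planned.

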### Sample size

The primary objective is to assess the safety and function of the FAST PV and mGFR Technology in hospitalized patients with heart failure. This is a phase II trial. It is planned to enroll 50 eligible patients. No formal hypothesis test is performed to assess the primary objective. This is justified as follows:

1. Both function and safety cannot be uniquely assessed by one specific endpoint, but there exist several relevant endpoints and endpoint-related criteria which must be investigated in order to assess the global function and safety.
2. For reasons of feasibility, the studies sample size is limited to 50 patients which is an adequate number in the context of a phase II trial. However, this limited number does not allow to address a complex multiple testing problem with adequate power.

Therefore, all analyses are purely descriptive.

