## **3 Trial centres**

50 patients with acute decompensated heart failure were enrolled at the Nephrology and Cardiology departments of Charité - Universitätsmedizin Berlin as well as at the Kerckhoff-Klinik Bad Nauheim.

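### The clinical model for plasma and blood volume is scored on the patients used to fit it: its zero mean difference is algebraic and its other agreement figures are modestly optimistic

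*SAP*

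**What the plan says.** SAP 7.7.1 first compares the published formulas with measured values. It uses Bland-Altman plots with fixed limits (300 mL either way for PV, 500 mL for TBV), the shares within 15% and 30% of the measured value, and a concordance-type accuracy index with a 95% confidence interval. The formulas' coefficients are printed in SAP 7.2 and are not estimated in this trial.

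The next objective is a fitted model: "To evaluate how a clinical evaluation on days 1 and 3 predicts mPV and mTBV at these time points, linear regression models will be used". For the covariates, "the following parameters will be considered for the analysis in the order of appearance", and "BMI, weight, height will be entered in 3 separate models". Each estimated parameter requires ten observations. The scoring is one sentence: "Bland-Altman plots, frequencies within 15% and 30%, and diagnostic accuracy will be evaluated as stated before".

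SAP 8 drops the protocol's variable selection in favour of a fixed, ordered covariate set. On size, "It is planned to enroll 50 eligible patients" (SAP 1.2), and SAP 3 reports that "50 patients with acute decompensated heart failure were enrolled". SAP 7.5 provides for missing second doses, so day 3 may have fewer. Neither document mentions a hold-out set, cross-validation, bootstrap correction or external data.

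**The concern.** The same measures are applied to two different things. A published formula meets these patients for the first time, so its mean difference, spread and concordance estimate how it performs in them. The clinical model has already been tuned to the values it is judged against, so its scores describe fit, although the stated question is how well clinical evaluation predicts volume.

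The two sets of results will sit in one section of the report in the same units. A reader will compare them, and will see a mean difference of zero for the clinical model beside a non-zero one for each formula. SAP 7.1 says the results are meant to generate hypotheses for phase III, so optimistic figures would be carried forward.

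**Working it through.** **Plan's own figure.** There is none to reproduce. The SAP gives no performance target for the clinical model, and 50 is a feasibility number with no alpha, power or SD behind it.

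**Model size.** The ten-per-parameter rule gives 50/10 = 5 parameters, or 40/10 = 4 if only 40 patients contribute. The SAP does not say whether the intercept counts, so at n = 50 both p = 5 (intercept plus four covariates) and p = 6 were examined.

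**Mean difference.** Least squares with an intercept forces the residuals to sum to zero. The mean of fitted minus measured is therefore 0 in any data set. In every simulated trial it was zero to rounding error.

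**Limits of agreement.** Let σ be the residual SD.
- In-sample SD of differences: σ√[(n−p)/(n−1)].
- Root mean square error in new patients (random covariates): σ√[(1+1/n)(n−2)/(n−p−1)].
- n = 50, p = 5: √(45/49) = 0.958 and √(1.02×48/44) = 1.055. Ratio 0.908, so about 9% too narrow.
- n = 50, p = 6: √(44/49) = 0.948 and √(1.02×48/43) = 1.067. Ratio 0.888, about 11%.
- n = 40, p = 4: √(36/39) = 0.961 and √(1.025×38/35) = 1.055. Ratio 0.911, about 9%.

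**Other measures.** These need assumptions that the documents do not supply. For each scenario, 1,500 trials were simulated with n = 50 and p = 5 (hematocrit, mean arterial pressure, weight, age). mPV was generated as the Kaplan-Hakim value plus noise, so the formula is correct on average. Covariate distributions and residual SDs are assumed. Entries are fitted model in-sample / fitted model in new patients / formula.

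| Residual SD (mL) | SD of differences (mL) | Within 15% (%) | Concordance |
|---|---|---|---|
| 150 | 153 / 170 / 149 | 98.9 / 98.0 / 99.1 | 0.915 / 0.909 / 0.918 |
| 300 | 292 / 320 / 299 | 87.0 / 83.4 / 86.0 | 0.848 / 0.837 / 0.845 |
| 500 | 481 / 525 / 498 | 66.2 / 61.5 / 64.4 | 0.776 / 0.759 / 0.769 |
| 700 | 668 / 734 / 695 | 51.6 / 46.8 / 49.4 | 0.728 / 0.702 / 0.716 |

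From 300 to 700 mL the within-15% share is inflated by 3.6 to 4.8 points and concordance by 0.011 to 0.026. At 500 mL the share within 300 mL is 47.0% in-sample and 42.9% in new patients, and the mean difference in new patients averages about 63 mL in absolute size instead of 0. With covariates unrelated to mPV, expected R² is 4/49 = 0.08, and concordance is 0.589 in-sample against 0.500 in new patients.

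**Ranking against the formula.** At 300, 500 and 700 mL the average order reverses: the fitted model is ahead in-sample and behind in new patients. This is a tendency. Across residual SDs of 150, 300, 500 and 700 mL, the fitted model beat the formula in-sample on SD in 31%, 73%, 89% and 93% of trials, on within-15% in 14%, 49%, 55% and 58%, and on concordance in 35%, 60%, 72% and 78%. In new patients it had the lower root mean square error in at most 0.5% of trials. When the formula was made wrong by 400 mL in either direction (residual SD 500 mL), the fitted model won on root mean square error in 100% of trials in-sample and in 99.9% in new patients.

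The within-30% share and mTBV were not simulated. The zero mean difference and the SD formulas do not depend on which outcome is modelled.

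**The case against.** The SAP has already removed the largest source of overfitting: it caps model size and drops variable selection. The figures above respect both rules, and what remains is modest. A concordance at n = 50 has a standard error of about 0.049 under no association (half the square root of 2(2n+5)/[9n(n−1)]), more than the roughly 0.02 of optimism. The no-signal case of 0.59 is not the likely one, because hematocrit and weight are inputs to the SAP's own plasma volume formula. In the 500 mL scenario, 47.0% and 42.9% within 300 mL lead to the same reading of poor agreement. No formal comparison of the clinical model with the formulas is planned, the objective is secondary, and all analyses are called descriptive. Optimism here also works against the trial's hypothesis that measured values differ from clinical assessment (protocol synopsis, Hypotheses).

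All of this stands, and it limits the severity. It does not remove the point. The descriptive label answers questions about testing, whereas the described estimate itself is biased. The planned interval reflects sampling error, and nothing in the SAP says it allows for coefficients estimated in the same patients. The zero mean difference is uninformative at any sample size.

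A reader might go further and infer that the fitted model must look better than the formulas by construction. The documents do not support that. Kaplan-Hakim multiplies weight by one minus hematocrit, Nadler uses height cubed, and the SAP enters BMI, weight and height in separate models, so the formulas are not special cases of the clinical model. Least squares does not optimise concordance or the within-15% share either.

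**Conclusion.** The point holds in a limited form. As written, the clinical model is scored in-sample; this is inferred from the absence of any validation step, but it is the natural reading. Its mean difference is zero by algebra. Its limits of agreement are about 9-11% too narrow; this depends only on n, p and standard linear-model assumptions. The inflation of about 4-5 points in the within-15% share and about 0.02 in concordance rests on the assumed residual SDs of 300-700 mL and the assumed covariate distributions.

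In-sample superiority over the formulas is made more likely but is not guaranteed. Nor may a reader dismiss any observed advantage as an artefact: if a formula is biased in this cohort, the fitted model's gain is real recalibration. Fifty patients is an upper limit, and day 3 may have fewer. Severity is minor to moderate.

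**What to change.** Add to SAP 7.7.1 that, for the clinical model, the Bland-Altman, within-15%/30% and accuracy results will be given both as apparent values and after bootstrap optimism correction (or repeated k-fold cross-validation), refitting the same fixed covariate set in each resample. Plain leave-one-out should not be used for concordance: it averaged 0.466 in the no-signal simulation, where 0.5 is correct.

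State in the SAP and report that the zero in-sample mean difference follows from the fitting method and is not a finding, and that the formulas were not refitted. Alternatively, also show the formulas after intercept-and-slope recalibration under the same resampling, which puts both approaches on equal terms. State whether the intercept counts towards the ten-per-parameter rule.

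The cost is a sentence or two in the SAP and a few lines of R, with no new data. The clinical model's reported figures will be slightly less favourable.
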